5 AMENDMENTS AND UPDATES

None

6 MILESTONES

Planned date
Q3, 2020
Q1, 2021
Q2, 2023
Q1, 2021
Q4, 2021; Q4, 2022
Q4, 2023 ¹

¹ Data updates have a lag period of up to 1.5 years. Data analysis and reporting will introduce a further lag of 6 months. Therefore, data included in the final report will likely be up to end of 2021.

7 RATIONALE AND BACKGROUND

Nocturia is defined as a complaint that an individual has to wake at night one or more times to void where each micturition is preceded and followed by sleep. Nocturia can be due to many factors, such as an underlying medical condition. However, some people experience nocturia due to idiopathic nocturnal polyuria, which means that although their total 24-hour production may remain normal, they produce an excessive amount of urine at night. Nocturia is a common cause of sleep disruption, and impaired sleep is associated with several serious short and long-term health effects. Studies have for example showed an association between sleep deprivation and obesity, diabetes, weakened immune system and some cancer types (1-5).

In 2016, Ferring Pharmaceuticals A/S, hereafter referred to as Ferring, finalised a decentralised procedure (DCP) in the European Union (EU) leading to the approval of NOCDURNA (desmopressin, gender-specific low doses of 25 μ g for women and 50 μ g for men) for the symptomatic treatment of nocturia due to idiopathic nocturnal polyuria in adults. The active substance in NOCDURNA oral lyophilizate is desmopressin as desmopressin acetate (hereafter referred to as desmopressin), a synthetic analogue of the naturally occurring vasopressin, an antidiuretic hormone that promotes water re-absorption by the kidneys. The antidiuretic effect arises from its binding to the V₂-receptors in the renal collecting tubule, which results in increased water re-absorption in the collecting duct of the kidney and reduced volume of urine. Due to the low gender-specific doses of 25 μ g for women and 50 μ g for men, and the limited duration of action of NOCDURNA, the antidiuretic activity is limited to the night time sleep period.

Some safety concerns relating to NOCDURNA were defined during the EU DCP; risk of hyponatraemia (especially in elderly patients aged ≥65 years), a potential risk of thromboembolic events (though only expected at doses much higher than those recommended for NOCDURNA), and a potential risk of acute exacerbation of congestive heart failure in patients with chronic cardiac insufficiency. These safety concerns were based on data from clinical trials in haemophilia (OCTOSTIM, high-dose trials), postmarketing experience and general knowledge about pharmacodynamics and physiology of desmopressin. More specifically, the antidiuretic effect of desmopressin might lead to water retention and subsequently hyponatraemia through dilution of serum, if fluid intake is not limited. In phase 3 clinical trials with NOCDURNA, the incidence rate of clinically significant hyponatraemia (<130 mmol/L) was 2-3% in both genders (6, 7). A meta-analysis of data from three clinical trials of desmopressin in nocturia identified age \geq 65 years, dose, low baseline serum sodium level and kidney function as significant risk factors for hyponatraemia in both sexes (8). This is similar to the risk factors associated with hyponatraemia in the general population. Furthermore, desmopressin at very high intravenous doses (equivalent to as much as 8,000 µg oral lyophilisate) increases the levels of some coagulation factors (factor VIII and von Willebrand factor) in the blood. Persistently increased endogenous factor VIII levels are a risk factor for venous thromboembolism (VTE). The evidence for elevated von Willebrand factor levels as a risk factor for VTE is less strong, but some studies have demonstrated an association (9). Finally, patients with heart failure already have abnormal water retention, hypo-osmolality,

and frequently hyponatraemia secondary to renal V₂-receptor activation. Due to the antidiuretic effect, desmopressin may lead to worsening of the fluid overload and to an increased risk of hyponatraemia in these patients. Consequently, heart failure is a contraindication to the use of NOCDURNA.

Against this background, the DCP member States have required that a post-authorisation safety study (PASS) is included in the NOCDURNA risk management plan to evaluate safety concerns and to collect long-term data in patients aged ≥65 years treated with NOCDURNA according to the approved summary of product characteristics (SmPC).

8 **RESEARCH QUESTION AND OBJECTIVES**

The overall objective of the present study is to increase the understanding of the long-term safety of NOCDURNA as used in routine clinical practice. This will be achieved by assessing the incidence risk and rate of hyponatraemia, cardiovascular (including acute exacerbation of congestive heart failure in patients with chronic cardiac insufficiency) and thromboembolic events among patients, in particular the elderly, treated with NOCDURNA. In addition, since it is desirable to put these observations into context and characterise a population with similar indications who do not receive desmopressin, a similar number of patients who are new users of standard care for other lower urinary tract symptoms (LUTS) will be evaluated in order to inform on the safety and utilisation of NOCDURNA.

Estimated incidence rates among NOCDURNA patients will be compared with incidence rates among a cohort of patients with newly initiated treatment for LUTS.

The **primary objective** is to

Estimate the incidence rate of symptomatic hyponatraemia (defined as a recorded diagnosis of hyponatraemia) among patients treated with NOCDURNA, and patients with LUTS separately, overall and by subgroups of interest (including elderly patients, aged \geq 65 years).

The secondary objectives are to:

- 1. Describe the demographic and health characteristics of the population receiving NOCDURNA and patients with LUTS, including prevalence of risk factors for outcomes of interest.
- 2. Estimate the incidence rate of hyponatraemia requiring hospital intensive care among patients treated with NOCDURNA and patients with LUTS separately.
- Estimate the incidence rate of clinically significant hyponatraemia (defined as a serum sodium concentration of <130 mmol/L) among patients treated with NOCDURNA and patients with LUTS separately.
- 4. Estimate the rate of all-cause mortality among patients treated with NOCDURNA and patients with LUTS separately.
- 5. Estimate the incidence rate of the following events of special interest among patients treated with NOCDURNA and patients with LUTS separately:
 - a. Major cardiovascular events (composite endpoint)
 - a. Major venous thromboembolic events (composite endpoint)
- 6. Estimate the incidence rate of acute exacerbation of congestive heart failure among patients who have chronic cardiac insufficiency treated with NOCDURNA, and patients with LUTS, separately.

7. In addition, a subgroup analysis of all patients adhering to the label as assessed by the proxy based on diagnosis and contra-indications (as available) will be conducted.

8.

- 9. Estimate the incidence rate of primary and secondary outcomes of interest between patients treated with NOCDURNA compared to a population of LUTS patients adjusted for confounding factors, by country where data available.
- 10. Estimate the incidence rate of cardiovascular and thromboembolic events of interest resulting in treatment withdrawal of NOCDURNA.

All secondary objectives will be evaluated in the overall population and among subgroups of interest (including elderly, aged ≥65 years).

9 **RESEARCH METHODS**

9.1 STUDY DESIGN

This is a multi-country, cohort study using secondary data collected from research databases and administrative national healthcare registries in selected European countries (Denmark, Germany and Sweden).

Cohorts of patients using NOCDURNA or treatment of LUTS (new user) will be identified from existing data sources in each country of study. These data sources hold information on dispensed prescriptions, patient demographics and diagnoses. The LUTS contextual cohort will be comprised of patients based newly starting treatments associated with polyuria, receiving relevant standard care. For secondary comparative analyses, the comparator group for NOCDURNA patients will be LUTS patients.

The study period will be from the date of launch of NOCDURNA until the date of latest data availability in each country, considering that the final study report is planned for 2023. Given the lag time of data updates and time allocated for analysis and reporting, last data included in the final report is likely to be up to end of 2021. Historical data, reflecting a minimum of 12 months before initiation of treatment with NOCDURNA (or initiation of treatment for LUTS), will be used to assess characteristics (e.g., demographics, indication, comorbidities and co-medication) at the index date.

In addition to the final study report, there will be annual interim reports (one per year) on study progress and any emerging safety data. Both country-specific and pooled results (meta-analysis) will be presented in the final report, where data are available.

9.2 SETTING

The study will be conducted among patients using NOCDURNA in the outpatient setting in three European countries: Denmark, Germany and Sweden. These countries have been selected following careful consideration of multiple factors: a feasibility assessment of the ability of candidate data sources to address the study objectives (please refer to section 9.5.2), recommendations by the Swedish Medical Products Agency (MPA), and expected uptake of NOCDURNA in the candidate countries. Sales data was used as an indicator of uptake of NOCDURNA to ensure a sufficiently large exposed population (Table 1). Based on the information contained in the data sources available in the candidate countries and the estimated extent of exposure to NOCDURNA based on available sales data in European countries, Denmark, Germany and Sweden were chosen as countries of study. **Table 1:** NOCDURNA sales statistics (2018) and launch dates in candidate countries of study

Country	Share of NOCDURNA sales in 2018 (%)	NOCDURNA commercial launch date
Germany	40	January 2017
United Kingdom	22	November 2016
Belgium	9	March 2017
The Netherlands	7	November 2016
Sweden	7	January 2017
Denmark	5	August 2017

9.2.1 Duration of the study

The planned study period ranges from the date of launch of NOCDURNA (Table 1) to the date of latest data availability in each country. Thus, the planned study periods are as follows:

- Denmark: 29 August 2016 to 31 December 2021
- Germany: 1 January 2017 to 31 December 2021
- Sweden: 20 January 2017 to 31 December 2021

Historical data, reflecting a minimum of 12 months before index date will be used to assess baseline characteristics (e.g., demographics, comorbidities and co-medications). Thus, the total period for which data will be collected is from at least 12 months before the date of launch of NOCDURNA to the date of latest data availability in each country.

9.2.2 Cohort entry

Cohort entry is marked by the index date.

9.2.2.1 Index date - NOCDURNA cohort

The index date is defined by their first ever prescription of NOCDURNA in the study time period.

9.2.2.2 Index date - LUTS cohort

The index date is defined by their first ever prescription of medication used to treat urinary frequency and incontinence (Anatomic Therapeutic Chemical (ATC) codes G04BD) or benign prostatic hypertrophy (ATC codes G04C) in the study time period.

9.2.3 Cohort exit

9.2.3.1 Right censoring events – NOCDURNA cohort

Patients will be followed from the index date to the date of a censoring event: a dispensed prescription for a vasopressin agonist or desmopressin drug other than NOCDURNA, transfer out of the database, emigration, death or end of the study period, whichever occurs first and irrespective of treatment status (on/off drug). As appropriate, patient will also be followed from index date to the date of the diagnosis of the outcome of interest, or end of treatment of NOCDURNA (+7 days) as defined in section 9.3.1.

9.2.3.2 Right censoring events – LUTS cohort

Patients will be followed from the index date to the date of the censoring event: a dispensed prescription for a vasopressin agonist or desmopressin drug, transfer out of the database, emigration, death or end of the study period, whichever occurs first. As appropriate, patient will also be followed from index date to the date of the diagnosis of the outcome of interest, or the end of treatment of drugs defining the LUTS cohort, as defined in section 9.3.1.

9.2.4 Eligibility criteria

9.2.4.1 Inclusion criteria – NOCDURNA cohort

The cohort of NOCDURNA patients will consist of individuals meeting the following inclusion criteria:

 A first-ever dispensed prescription for NOCDURNA [desmopressin; Anatomical Therapeutic Chemical (ATC) code: H01BA02; brand name: NOCDURNA; dose: 25 or 50 microgram] recorded in the relevant country-specific data source between its launch date and the latest date of data availability in each country

Note: To identify NOCDURNA dispensations, first all desmopressin dispensations with the ATC code H01BA02 will be extracted, then the cohort for analysis will be selected using the brand name NOCDURNA and the dose of NOCDURNA (25 or 50 microgram).

- Aged 18 years and above on the index date
- At least 12 months' registration in the relevant country-specific database(s) prior to the index date, to ensure a sufficiently long period of baseline data availability

9.2.4.2 Exclusion criteria – NOCDURNA cohort

The following exclusion criteria will be applied to the NOCDURNA cohort:

- Treatment with vasopressin or any of its analogues (defined as a dispensed prescription within 6 months before the index date [index date -1 day]; ATC codes H01BA), irrespective of formulation or dose/strength
- Multiple desmopressin drugs dispensed on the index date

9.2.4.3 Inclusion criteria – LUTS cohort

Patients meeting the following criteria will be included in the LUTS cohort:

- A first-ever dispensed prescription for a medication used to treat urinary frequency and incontinence (ATC codes G04BD) or benign prostatic hypertrophy (ATC codes G04C) between the launch date of NOCDURNA and the latest date of data availability in each country
- Aged 18 years and above at index date

The ATC codes used to define the LUTS cohort are summarized in Annex 3 Definitions (Table A1).

9.2.4.4 Exclusion criteria – LUTS cohort

The following exclusion criterion will be applied to the LUTS cohort:

• Treatment with vasopressin or any of its analogues (defined as a dispensed prescription within 6 months before the index date [index date -1 day]; ATC codes H01BA), irrespective of formulation or dose/strength

9.2.5 Subpopulations of interest

Elderly patients (≥65 years of age at index) will be considered a subpopulation of special interest, for which separate analyses will be performed.

Furthermore, the following patient groups will be considered as subpopulations of special interest, as they are contraindications for NOCDURNA use. Numbers permitting, sub-analyses will be performed according to the NOCDURNA and the LUTS group overall and by the elderly.

For the primary outcome:

- History of hyponatraemia
- Polydipsia
- Concomitant use of loop diuretics
- Concomitant use of glucocorticoids
- Congestive heart failure (chronic)
- Kidney disease (chronic kidney disease stage 3 and over)
- Syndrome of inappropriate antidiuretic hormone secretion (SIADH)

- Additionally, for the cardiovascular disease outcome: uncontrolled hypertension
- Additionally, for the thromboembolic event outcome: coagulation disorders

See Annex 3, Table A2 for diagnostic codes.

9.3 VARIABLES

9.3.1 Exposure

Person-time observed from index date to the date of outcome or censoring event will be determined for both the NOCDURNA group and the LUTS group.

Person-time exposed will start accumulating from the index date. For the NOCDURNA group this will be the date that the first-ever prescription for NOCDURNA was dispensed. Thus, this study will include patients who are new users of NOCDURNA. For the LUTS group, this will be the date of a first-ever prescription of a drug with the ATC code G04BD or G04C within the study time period. Thus, the LUTS groups will include patients who are new users of treatments for lower urinary tract symptoms.

Specific episode of exposure to NOCDURNA will be established using information on dispensed prescriptions for NOCDURNA. Information will include drug and substance name, ATC code, formulation, strength and dispensed amount of drug, as available in each data source.

On-treatment person-time will be constructed from single prescriptions or multiple sequential prescriptions for NOCDURNA and the drugs defining the LUTS cohort. The duration of individual prescriptions for NOCDURNA will be calculated based on the days supplied, as estimated from the number of oral lyophilisates dispensed and the recommended daily dosage, one oral lyophilisate per day. The estimated end date of a prescription will be the date it was dispensed plus the days supplied. Sequentially dispensed prescriptions for NOCDURNA will be bridged into continuous on-treatment episodes if each subsequent date the drug was dispensed was within the days supplied by the preceding prescription plus a period equivalent to the days supplied multiplied by 2 (*i.e.*, the permissible gap). In case of prescription overlaps, the number of overlapping days will be added to the estimated end date of the subsequent prescription. The first treatment period will end when there is no subsequent prescription dispensed within the days supplied from the preceding prescription plus the defined permissible gap. Prescriptions of LUTS-defining drugs (ATC code G04BD or G04C) will be treated analogous to NOCDURNA in terms of permissible gap. Treatment restarts following treatment holiday will not be evaluated in this study.

9.3.2 Outcomes

The primary and secondary outcomes presented below are also summarized in Table 2.

9.3.2.2 Secondary outcomes

The secondary outcomes for this study are the following events:

1. Hyponatraemia requiring hospital intensive care, defined as a primary or secondary diagnosis of hyponatraemia (ICD-10: E87.1) recorded in an intensive care unit.

This outcome will only be evaluated in Sweden using data collected from the Swedish Intensive Care Registry (SIR; see section 9.4.3.4), as information to distinguish between hospital inpatient care in general and intensive care in particular is not available in the Danish national registries or the German GePaRD (see sections 9.4.1 and 9.4.2, respectively).

Only incident events (first hyponatraemia record from within hospital intensive care during follow-up) will be considered.

2. Clinically significant hyponatraemia, defined as a serum sodium concentration of <130 mmol/L (10).

In addition, hyponatraemia by level of severity will be evaluated, where *mild* hyponatraemia is defined as a serum sodium concentration of 130-<135 mmol/L, *moderate* as a serum sodium concentration of >125-<130 mmol/L, and *severe* as a serum sodium concentration of $\leq 125 \text{ mmol/L}$.

Clinically significant hyponatraemia, including level of severity, will only be assessed in Denmark using data collected from the Danish National Laboratory Database Research Table. The evaluation of this outcome will be restricted to patients residing in the four Danish regions covered by the database (see section 9.4.1.4).

Incident and recurrent events will be considered and analysed separately.

3. All-cause mortality, defined as death from any cause.

This outcome can be evaluated in all data sources: Denmark and Sweden using the national cause of death registries (see sections 9.4.1.5 and 9.4.3.5), and in Germany using the date of death.

4. Major adverse cardiovascular events (MACE (11)), defined as a record of myocardial infarction and stroke, (see Annex 3, Table A3, for a list of diagnosis codes used to define these conditions) recorded in each relevant country data source. In Sweden and Denmark, fatal events of myocardial infarction and stroke are also considered as MACE (as cause of death is available). MACE is a composite endpoint.

In addition to overall MACE events, MACE requiring hospital intensive care defined as defined as a primary or secondary diagnosis of MACE recorded in a hospital intensive care unit will be reported in Sweden.

5. Major venous thromboembolic (VTE) events, defined as a record of a deep vein thrombosis, pulmonary embolism or portal vein thrombosis (see Annex 3, Table A3, for a list of diagnosis codes used to define these conditions) recorded in each relevant country data source. In Sweden and Denmark, fatal events of VTE are also considered (as cause of death is available). VTE is a composite endpoint.

In addition to overall VTE events, VTE events requiring hospital intensive care defined as defined as a primary or secondary diagnosis of VTE events recorded in a hospital intensive care unit will be reported in Sweden.

Fatal and non-fatal MACE and VTE events will be assessed separately. Fatal events will only be assessed in Denmark and Sweden using the national registries. Information on cause of death is not available in the German GePaRD. For fatal events, death from a MACE or VTE event recorded as the underlying or contributory cause will be considered. For non-fatal MACE and VTE events, primary and secondary diagnoses will be considered equally important (in Germany: discharge diagnoses). Incident events of MACE and VTE in the study time period will be analysed.

6. Acute exacerbation of congestive heart failure

Given that cardiac insufficiency is a contraindication for the use of NOCDURNA, the incidence of acute exacerbation of congestive heart failure among patients who

have chronic cardiac insufficiency is considered an exploratory outcome in this study.

This outcome will only be analysed among patients with prevalent chronic heart failure. Prevalent chronic heart failure will be defined as ever having had a primary or secondary diagnosis of heart failure (ICD-10: I50; in German GePaRD: outpatient or inpatient diagnosis) before the index date, but no recorded primary diagnosis of heart failure from hospital inpatient care or the acute and emergency ward in the 6 months prior to the index date (German GePaRD: discharge diagnoses). Among these patients, acute exacerbation of heart failure from hospital inpatient care or the acute and emergence as a primary diagnosis of acute or acute-on chronic heart failure from hospital inpatient care or the acute and emergency ward, or death from heart failure as the underlying or contributory cause. Non-fatal events of acute exacerbation of heart failure as the underlying will be evaluated in all three countries, while fatal events will only be evaluated in Denmark and Sweden.

In addition, a subgroup analysis of all patients adhering to the label as assessed by the proxy based on diagnosis and contra-indications (as available) will be conducted.

7. MACE and VTE events resulting in treatment withdrawal of NOCDURNA

Serious events resulting in treatment withdrawal of NOCDURNA will be evaluated in the NOCDURNA exposed group only. Treatment cessation of NOCDURNA, defined by a time after prescription longer than the permissible gap (see section 9.3.1), will be defined as the end of an on-treatment period. Serious events will be evaluated in 14 days prior to the treatment cessation date.

Serious MACE and VTE events will be defined as a primary or secondary diagnosis of MACE or VTE recorded in a hospital intensive care unit. This can be only evaluated in Sweden.

Variable	Definition	Countries in which outcome assessed		
Primary outcome				
Symptomatic hyponatraemia	Primary or secondary diagnosis of hyponatraemia (E87.1)	 Denmark Germany (hospital discharge diagnosis) Sweden 		
Secondary outcomes				

Table 2: Definitions of primary and secondary outcome variables

Post Authorization Safety Study (PASS) Protocol Study Number: 000248

Variable	Definition	Countries in which outcome assessed
Hyponatraemia requiring hospital intensive care	Primary or secondary diagnosis of hyponatraemia (E87.1) from hospital intensive care	Sweden
Clinically significant hyponatraemia including hyponatraemia by severity	Serum sodium concentration <130 mmol/L Mild hyponatraemia: serum sodium concentration 130-<135 mmol/L Moderate hyponatraemia: serum sodium concentration >125-<130 mmol/L Severe hyponatraemia: serum	• Denmark
All-cause mortality	sodium concentration ≤125 mmol/L Death from any cause	DenmarkSwedenGermany
Major cardiovascular events	Primary or secondary diagnosis of cardiovascular death (underlying or contributory cause), myocardial infarction or stroke	 Denmark Germany (non-fatal events only; discharge diagnosis) Sweden
Major venous thromboembolic events	Primary or secondary diagnosis of deep vein thrombosis, pulmonary embolism, portal vein thrombosis, or death from either of these conditions as the underlying or contributory cause	 Denmark Germany (non-fatal events only; discharge diagnosis) Sweden
Acute exacerbation of congestive heart failure	Primary diagnosis of acute or acute- on-chronic heart failure from hospital inpatient care or the acute and emergency ward, or death from heart failure as the underlying or contributory cause	 Denmark Germany (non-fatal events only; discharge diagnosis) Sweden
Serious adverse events	Primary or secondary diagnosis of MACE or VTE leading to admission to a hospital intensive care unit	Sweden

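### Acute exacerbation of heart failure (exploratory outcome, Denmark and Sweden): the fatal part accepts heart failure as a merely contributory cause, with no acuity condition, in a cohort that already has the diagnosis

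*Protocol*

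**What the plan says.** Section 9.3.2.2, outcome 6, fixes the population first: "This outcome will only be analysed among patients with prevalent chronic heart failure". Entry depends on history: "Prevalent chronic heart failure will be defined as ever having had a primary or secondary diagnosis of heart failure" (I50) before the index date, with no primary heart-failure diagnosis from inpatient or emergency care in the 6 months before index.

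Within that cohort there are two ways to have an event:

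- Non-fatal: a "primary diagnosis of acute or acute-on chronic heart failure from hospital inpatient care or the acute and emergency ward".
- Fatal: "or death from heart failure as the underlying or contributory cause".

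Table 2 repeats the fatal limb ("emergency ward, or death from heart failure as the underlying or contributory cause"), so it is not a slip in one place. SAP section 10.2.7 carries the same rule. Annex 3, Table A3, gives the heart-failure outcome code as I50 alone, without an acute subcode.

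Non-fatal events are evaluated in all three countries, "while fatal events will only be evaluated in Denmark and Sweden". The section also gives the status of the outcome: its incidence among patients who "have chronic cardiac insufficiency is considered an exploratory outcome in this study".

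For the other two composites the same section says that "Fatal and non-fatal MACE and VTE events will be assessed separately". It says nothing equivalent for heart failure. Section 9.7.2.8 sends the outcome to the Poisson incidence-rate analysis used for the primary outcome, and section 9.7.2.9 extends the NOCDURNA/LUTS comparison to the secondary outcomes.

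**The concern.** The two limbs measure different things. The non-fatal limb asks for acuity and for the primary diagnostic position. The fatal limb asks for neither, and it relies on the same diagnosis that brought the patient into the cohort. A patient with long-standing heart failure who dies of another disease, with heart failure recorded as contributing, meets the event definition even if the heart failure did not acutely worsen.

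The underlying-or-contributory convention is less troublesome for MACE and VTE. Infarction, stroke and embolism are discrete events, and they do not define entry to the cohort. Here the convention is applied to a chronic condition that every patient has at baseline.

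Three things are at stake. The absolute exacerbation rate in Denmark and Sweden may be too high. The IRR is mixed with the ratio for deaths that need not reflect fluid retention, the mechanism behind the concern in section 7. If those deaths are about equally frequent in the two groups, a real excess is diluted, which is the unsafe direction in a safety study. Finally, the outcome under one name has a different content in Germany.

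**Working it through.** The protocol gives no event count, rate or power for this outcome, so there is no figure to reproduce. The check is a comparison of definitions, followed by an illustration on assumed rates.

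**Definitions side by side (Protocol 9.3.2.2, Table 2, Table A3)**

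| | Acuity required | Position required | Countries |
|---|---|---|---|
| Cohort entry | no | primary or secondary | all three |
| Non-fatal event | yes | primary | all three |
| Fatal event | no | underlying or contributory | Denmark, Sweden |

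I found no acuity condition for the fatal limb elsewhere in the protocol. The limitations in section 9.9 note that cause-specific death is missing in Germany, but do not mention this misclassification.

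**Illustration (all rates assumed, none from the documents)**

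Let *a* be the true exacerbation rate per 1000 person-years. Let *c* be the rate of first counted events that are contributory-only deaths without an exacerbation. Let *r* be the NOCDURNA/LUTS ratio for those deaths.

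- Inflation of the rate = (a + c)/a
- Share of counted events that are not exacerbations = c/(a + c)
- Observed IRR = (IRR × a + r × c)/(a + c), with a and c taken in the LUTS group

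With r = 1:

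| a | c | Inflation | Share not exacerbations | Observed if true IRR 1.5 | Observed if true IRR 2.0 |
|---|---|---|---|---|---|
| 50 | 10 | 1.20 | 17% | 1.42 | 1.83 |
| 50 | 25 | 1.50 | 33% | 1.33 | 1.67 |
| 50 | 50 | 2.00 | 50% | 1.25 | 1.50 |
| 100 | 10 | 1.10 | 9% | 1.45 | 1.91 |
| 100 | 25 | 1.25 | 20% | 1.40 | 1.80 |
| 100 | 50 | 1.50 | 33% | 1.33 | 1.67 |

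For example, with a = 50 and c = 25: (50 + 25)/50 = 1.50; 25/75 = 33%; (2 × 50 + 25)/75 = 1.67.

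Because only first events count, *c* excludes deaths after an exacerbation that has already been counted. Adding the total rate of contributory-only deaths to *a* would overstate the effect somewhat.

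**The case against.** The strongest reply is that the rule is deliberate. The protocol uses underlying or contributory cause for every fatal outcome, and a sensitive case definition is defensible in a safety study. Restricting to underlying cause would lose true fatal decompensations that were certified under another cause and had no qualifying admission. This stands as a real trade-off, and it is why the broad definition should be kept as a sensitivity analysis. It does not justify merging such deaths with acute events in one undivided rate.

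The exploratory label also stands, and it limits the weight of the point.

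A reader might infer that a contributory heart-failure entry in this cohort mostly restates the entry diagnosis, so that most such deaths are false events. The documents say nothing about certification practice, and some of these deaths will be true exacerbations. A reader might likewise infer that the IRR drifts towards the all-cause mortality ratio. Only deaths with heart failure recorded as a cause are added, so the pull is towards the ratio for those deaths.

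A reader might also conclude that the pooled estimate must be corrupted. Section 9.7.4 limits meta-analysis to outcomes definable in all three countries, which the fatal limb is not, and section 9.9.2 discloses the German gap. SAP Table 5 marks pooling of this outcome only as a possibility, although SAP section 10.5 lists it among the pooled outcomes. What is missing is an explicit statement that pooling uses the non-fatal component.

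**Conclusion.** The point holds as a defect of definition in an exploratory outcome. Applied as written, the fatal limb can count deaths from other causes in Denmark and Sweden as acute exacerbations, and this outcome lacks the fatal/non-fatal separation given to MACE and VTE. The direction for the absolute rate is upward. For the IRR it is towards the ratio for contributory-only deaths, which means dilution of an excess if that ratio is near 1.

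The size is unknown. The range of 1.10 to 2.00 for the rate, and of 1.50 to 1.91 for a true IRR of 2, rests wholly on assumed rates and on r = 1. A smaller *c* would give a smaller effect. The figures show how the error works and are not an estimate for this study. A correction is worth making because it is cheap, not because a large bias has been shown.

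**What to change.** In section 9.3.2.2 and Table 2, and correspondingly in SAP section 10.2.7:

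- In the main analysis, count a fatal event only when heart failure is the underlying cause of death.
- Report non-fatal, underlying-cause and contributory-only events separately, in line with the fatal/non-fatal split for MACE and VTE.
- Keep the present broad definition as a sensitivity analysis in Denmark and Sweden.
- State that cross-country pooling uses the non-fatal component only.

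A rule that also admits contributory-cause deaths shortly after an acute admission, such as within 30 days, is not needed. A qualifying admission after index is already the patient's incident event. A primary heart-failure admission in the 6 months before index excludes the patient from this cohort.

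The cost is a change to the definition and some extra table rows, using cause-of-death positions on which the protocol already relies in both countries. The main analysis will have somewhat fewer events and a slightly wider interval, and some true fatal decompensations certified under another underlying cause will appear only in the sensitivity analysis and the contributory-only count.
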